## 9.5 Exploratory Efficacy Analysis

The influence of site and other potentially prognostic baseline factors on treatment group differences in the desensitization response rate and MTD at Exit DBPCFC will be explored using the ITT population.

The factors to be explored will be:

- MTD of peanut protein at Screening DBPCFC, in log10 scale
- Age
- Presence of asthma, as recorded as part of allergy history
- Presence of allergic rhinitis or hay fever, as recorded as part of allergy history
- History of allergy to a food other than peanut, as recorded as part of the diet and non-peanut allergy history
- Severity of the peanut allergy, defined as the number of anaphylactic reactions to peanut experienced, divided by the duration of the peanut allergy, and categorized into: subjects with 0 anaphylactic reactions, those with at least one reaction but less than 1 every 5 years, and those with more than 1 reaction every 5 years
- Duration of peanut allergy in months, as recorded as part of allergy history
- Study site
- Peanut IgE level at baseline, in log10 scale
- Maximum SPT peanut wheal diameter at baseline
- VAS score at baseline
- BMI at baseline

If necessary, categorical variables will be pooled such that each pooled level will have at least 3 observations for each treatment group.

For nominal categorical variables, pooling will start with the smallest level which will be pooled with the next larger level until each pooled level has 3 observations for each treatment group. For ordinal categorical variables, pooling will proceed in the same manner but will start with the minimum ordinal value and pool in ascending order. Ties will be broken by sorting (in ascending order) the desensitization rate for CPNA, then by the desensitization rate for placebo, then by the geometric mean of the MTD for CPNA, and then by the geometric mean of the MTD for placebo. If the tie is still not broken, then tied levels (that are subject to pooling) are pooled together as the initial step.

If model parameters for a categorical variable are not estimable, then the minimum number of observations of 3 observations per pooled level for each treatment group will be increased by 1 in the above pooling algorithm until the model parameters are estimable. If the model parameters for a binary categorical variable are not estimable, then that factor will not be explored for its effect.

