#### 9.5.1 Effect on Desensitization Response Rate

The influence of these factors on treatment group differences in the desensitization response rate will be explored using logistic regression. These analyses will be performed on the ITT population.

The logistic regression model will include terms for treatment group and the baseline factor to be explored (e.g. site), and an interaction term between the baseline factor with treatment group. The odds ratio for the treatment group effect will be calculated at each level for categorical variables. The odds ratio for the treatment group effect will be calculated at 3 values for continuous variables (the 25% percentile, median, and 75% percentile). Main effects for treatment group and the baseline factor will also be calculated after dropping the interaction term from the model. A 95% confidence interval and p-value will be presented for each odds ratio using the Wald statistic. The p-value for the interaction term will also be presented and based on the Wald statistic.

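### The rule in SAP 9.5 for non-estimable models drops binary factors from the exploratory logistic analysis because of the observed responses; Firth penalized likelihood would keep those that meet the minimum cell size

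*SAP*

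**What the plan says.** SAP 9.5 lists twelve baseline factors. Three are plainly yes/no: "Presence of asthma, as recorded as part of allergy history"; "Presence of allergic rhinitis or hay fever, as recorded as part of allergy history"; and "History of allergy to a food other than peanut, as recorded as part of the diet and non-peanut allergy history".

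Before modelling, "categorical variables will be pooled such that each pooled level will have at least 3 observations for each treatment group". If a model still cannot be estimated, the remedy depends on the type of factor:

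- **More than two levels:** the minimum count "will be increased by 1 in the above pooling algorithm until the model parameters are estimable".
- **Two levels:** "If the model parameters for a binary categorical variable are not estimable, then that factor will not be explored for its effect".
- **Continuous:** no rule is given.

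SAP 9.5.1 specifies the response-rate model: "The logistic regression model will include terms for treatment group and the baseline factor to be explored (e.g. site), and an interaction term" between factor and treatment. A main-effects model is also reported, with the interaction removed. On inference: "A 95% confidence interval and p-value will be presented for each odds ratio using the Wald statistic". SAP 9.5.2 repeats the scheme for maximum tolerated dose with a discrete hazards model. Neither section defines when a model counts as not estimable, and neither offers a penalized, exact or likelihood-ratio alternative.

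**The concern.** A rule that removes a factor because too few subjects have it depends only on baseline data. This rule goes further. The minimum of 3 per cell already deals with sparse baseline data, so what remains to trigger the rule in SAP 9.5.1 is the pattern of responses.

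Whether asthma, rhinitis or other food allergy appears in Table 14.2.19 would then depend on the trial's results. A low placebo rate makes omission more likely, and SAP 4 plans for a placebo rate of 25% or less among those challenged. If no placebo subject responds, maximum likelihood gives no finite treatment odds ratio for any factor, including the continuous ones.

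**Working it through.** **1. Inputs.** SAP 4 gives about 50 subjects, 1:1, hence 25 per arm, and effective ITT response rates of 22% (placebo) and 58.7% (CPNA), or 20% and 56.6%. SAP 9.5 gives the minimum of 3. The following are assumptions: factor prevalence π of 20%, 30% or 40% (by symmetry also 80%, 70% or 60%); a response rate unrelated to the factor; and alternative placebo rates of 10% and 5%, which satisfy the plan's upper bound but are not planning values.

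**2. The plan's own figures.** Effective rates: 0.25 × 22/25 = 0.22; 0.667 × 22/25 = 0.587; 0.25 × 20/25 = 0.20; 0.7075 × 20/25 = 0.566. Exact enumeration of the Pearson chi-square test with 25 per arm gives power of 80.0% (22% vs 58.7%) and 80.2% (20% vs 56.6%). The stated power of at least 80% reproduces. The documents give no figure for the exploratory models.

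**3. Why only the responses can break the model.** With a binary factor, the intercept, treatment, factor and interaction are four parameters for four cells, so the model is saturated. With at least 3 subjects in every cell the design has full rank. Each fitted cell log-odds equals the observed log-odds, which is infinite if the cell has 0% or 100% responders and finite otherwise.

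**4. Formula.** A cell of m subjects with response rate p is usable with probability

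g(m, p) = 1 − p^m − (1 − p)^m.

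For one arm, summing over k = 3 to 22 subjects with the factor:

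A(p) = Σ Bin(k; 25, π) · g(k, p) · g(25 − k, p), and B = Σ Bin(k; 25, π).

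P(factor lost | minimum met) = 1 − A(p placebo) · A(p CPNA) / B².

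**5. One fixed split as an example.** Take 20 and 5 subjects per arm at 22% vs 58.7%. The chances of a degenerate cell are 0.007 (placebo, 20), 0.289 (placebo, 5), about 0 (CPNA, 20) and 0.082 (CPNA, 5). P(lost) = 1 − 0.9931 × 0.7108 × 1.0000 × 0.9183 = 0.35. A 15/10 split gives 0.11.

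**6. Averaged over cell sizes.**

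| Placebo vs CPNA | π = 20% | π = 30% | π = 40% |
|---|---|---|---|
| 22% vs 58.7% | 37% | 22% | 14% |
| 10% vs 58.7% | 67% | 57% | 51% |
| 5% vs 58.7% | 87% | 82% | 80% |

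The chance that no placebo subject responds is 0.90^25 = 7% at a 10% rate and 0.95^25 = 28% at 5%.

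**7. What the rule discards, and what Firth gives.** Take an illustrative table: placebo 5/15 with the factor and 0/10 without; CPNA 9/15 and 6/10.

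- **Maximum likelihood, interaction model:** diverges, with standard errors of about 94,000 and a Wald interaction p of 0.9998.
- **Maximum likelihood, main-effects model:** estimable, with treatment log-odds ratio 1.86 (SE 0.66).
- **Firth, interaction model:** in a saturated logistic model this amounts to adding 0.5 to each count. The treatment odds ratio is (9.5/6.5)/(5.5/10.5) = 2.8 with the factor and (6.5/4.5)/(0.5/10.5) = 30.3 without, the latter with a profile interval of 2.6 to about 4,290. The interaction log-odds ratio is ln 2.79 − ln 30.33 = −2.39, penalized likelihood-ratio p = 0.11.
- **Firth with placebo 0/25:** still finite, with odds ratios of 45.3 and 30.3.

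**The case against.** The strongest reply is that nothing confirmatory rests on this. SAP 9.5 is labelled exploratory, the primary test is a chi-square or Fisher's exact test, and the key secondary endpoints are tested in their own hierarchy. The rule is pre-specified and the factors are listed, so a missing row would be visible. All of that stands and sets the weight of the point. Pre-specification does not, however, make the omission independent of the outcome.

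A reader might infer that a factor vanishes precisely when its observed pattern is most extreme. The figures do not support that. Many losses come from very small cells: at 22%, a placebo cell of 3 has no responders with probability 0.78³ = 47%, and a cell of 5 with probability 0.78⁵ = 29%. At 20% prevalence and the planning rates, the largest degenerate cell has 5 or fewer subjects in 74% of losses. That share falls to 9% at 40% prevalence, so the objection weakens for more balanced factors.

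A reader might also infer that penalization keeps every factor at little cost. It does not. At 20% prevalence about 19% of factors fall below 3 in some cell whatever the responses, and the pooling rule then collapses them. Nor is the shrinkage slight in a separated cell: the estimate is finite only because of the penalty, as the interval of 2.6 to about 4,290 shows.

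Finally, the SAP does not say whether failure of the interaction model also removes the main-effects model. Its wording, that the factor is not explored, suggests that it does. This is an ambiguity to settle, not a proven loss.

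**Conclusion.** The point holds as a cheap improvement to an exploratory analysis. For a binary factor with at least 3 subjects in each cell, the SAP 9.5 rule is triggered in the 9.5.1 interaction model only by a cell with no responders or only responders, so omission depends on the outcome. The chance per factor is 14% to 37% at 22% vs 58.7%, and 51% to 67% if placebo response is 10%. These figures rest on assumed prevalences of 20% to 40%, 25 per arm, a response rate unrelated to the factor, and reading *not estimable* as the absence of a finite maximum likelihood solution.

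The documents do not support reading this as a threat to the primary or key secondary results.

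**What to change.** In SAP 9.5 and 9.5.1:

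- Define *not estimable*, for example as complete or quasi-complete separation or a rank-deficient design.
- Fit the logistic models by Firth penalized likelihood, with penalized profile-likelihood intervals and penalized likelihood-ratio p-values in place of Wald statistics. Apply this to continuous factors too.
- Replace the rule that drops binary factors, for those that meet the minimum of 3 per cell. Report the penalized fit and flag separated cells.
- State that the main-effects model is kept whenever it is estimable.

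In SAP 9.5.2, apply the same penalization to the discrete hazards model or keep a stated fallback. Changing to profile-likelihood intervals alone is not enough, because it does not give a finite hazard ratio under separation.

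For 9.5.1 the cost is a software option and one SAP paragraph; the hazards model may need extra programming. The statistical cost is that estimates for separated cells are finite only through the penalty and have very wide intervals, which the report should say. Factors with fewer than 3 subjects in a cell are still lost.

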#### 9.5.1 Effect on Desensitization Response Rate

The influence of these factors on treatment group differences in the desensitization response rate will be explored using logistic regression. These analyses will be performed on the ITT population.

The logistic regression model will include terms for treatment group and the baseline factor to be explored (e.g. site), and an interaction term between the baseline factor with treatment group. The odds ratio for the treatment group effect will be calculated at each level for categorical variables. The odds ratio for the treatment group effect will be calculated at 3 values for continuous variables (the 25% percentile, median, and 75% percentile). Main effects for treatment group and the baseline factor will also be calculated after dropping the interaction term from the model. A 95% confidence interval and p-value will be presented for each odds ratio using the Wald statistic. The p-value for the interaction term will also be presented and based on the Wald statistic.

#### 9.5.2 Effect on Maximum Tolerated Dose at Exit DBPCFC

Each baseline factor, other than peanut MTD at Screening DBPCFC (since it is already included as a covariate) will independently be evaluated using the discrete hazards model described in Section 9.3.1. Terms for treatment, MTD of peanut protein at the Screening DBPCFC in the log10 scale, the baseline factor to be explored (e.g. site), and an interaction term between the baseline factor with treatment will be included. The hazard ratio for the treatment effect will be calculated at each level for categorical variables. The hazard ratio for the treatment effect will be calculated at 3 values for continuous variables (the 25% percentile, median, and 75% percentile). Main effects for treatment and the baseline factor will also be calculated after dropping the interaction term from the model. A 95% confidence interval and p-value will be presented for each hazard ratio using the Wald statistic. The p-value for the interaction term will also be presented and based on the Wald statistic.

## 9.6 Interim Analysis

There is no interim analysis of efficacy planned for this study.

#### 9.7 Data Monitoring Committee

The DMC will meet regularly to review safety data, as described in the DMC Charter.

#### **10 SAFETY ANALYSES**

Unless otherwise noted, the Safety population will be used for all summaries of safety parameters. Safety listings will include all subjects in the Enrolled population, sorted by treatment received (CPNA then PBO), with subjects who did not receive any study product (NONE) at the end of the listing.

#### **10.1 Study Treatment Exposure**

Randomized study treatment is administered both in-clinic (for escalation dosing) and at home. Food product administered at a DBPCFC is not considered randomized study treatment.

Subjects receive randomized study treatment at Visit 01 and regularly scheduled Up-dosing Visits as described in Section 3.2.2. All randomized study treatment, whether for in-clinic or at home use, will be dispensed from the unblinded pharmacist or dietician, and be recorded using the dispensing record in TEMPO. Each bottle of randomized treatment dispensed will also be tracked with a treatment returned record in TEMPO, even if 0 capsules were returned. Most visits will include both a dispense record for a small number of capsules for the in-clinic up-dosing, and a subsequent dispense record for the entire amount of capsules given to the subject for at-home use, both on the same day. Therefore, dispense and return records will be matched by sorting both sets of records by subject, date, and capsule quantity.

If subjects return a bottle at a later visit, it will be assumed that the capsules were ingested during the time period for which it was initially dispensed. These return records will be matched to the correct dispense record using a combination of amounts of capsules returned, date returned, and the date dispensed.

If a subject does not return a bottle, the reason not returned (lost, destroyed, and other) will be recorded and numbers of capsules returned will be missing.

The average dose per day during each nominal dosing period (e.g., the 3 mg dosing time period, the 6 mg dosing time period, etc.) will be calculated as the total dose consumed during that period, divided by the number of days at that dose (defined as last date - first date + 1, for that period). First and last dose dates for each period will be determined based on a combination of in-clinic dosing (occurring on the day that study product was dispensed) and the dosing diary entries occurring

on or after the date that study product was dispensed for that period, and on or before the date that study product was returned. Any study product taken after Exit DBPCFC will be excluded from these calculations. Specifically:

- If the nominal dosing period begins with in-clinic dosing, such as for a dose escalation, the first dose date will be the dose date recorded on the in-clinic dosing CRF page, and the last dose date will be the last dose date recorded in the dosing diary prior to a dose change (if present), prior to an Exit DBPCFC (if no further dose changes are present), or prior to the end of the study (if no further dose changes are present and an Exit DBPCFC is not performed).
- If the nominal dosing period does not begin with in-clinic dosing, the first dose date will be the earliest dose date recorded in the dosing diary, after the date on which that dose of study product was dispensed.

If a subject titrates to a higher dose then is decreased back to an earlier dose, the average daily doses for the two periods at that dose level will be listed separately but combined for summaries. The combined average daily dose will be calculated as the total dose for both periods, divided by the total number of days across both periods. If a subject has 3 or more distinct time periods at the same dose level, they will be presented similarly.

The duration of treatment will be calculated as (date of last randomized study treatment administration– date of first randomized study treatment + 1). The duration of treatment in weeks will be calculated as the duration of treatment in days, divided by 7.

The overall duration of treatment, in weeks, will be summarized continuously by treatment. The overall treatment duration, in days, will be summarized by 30 day increments:  $\leq$  30 days, 31 – 60 days, ... 241 – 270 days, and >270 days. Duration will be listed by subject in both weeks and days.

The maximum dose achieved will be listed, and summarized both continuously and categorically by treatment group. The categorical summary will display the number of subjects whose highest dose is 0.5, 1, 1.5, 3, 6, 12, 20, 40, 80, 120, 160, 200, 240, or 300 mg/day. The last dose achieved, defined as the assigned dosage from the last bottle dispensed prior to Exit DBPCFC, will be listed and summarized similarly.

A dose escalation will be identified as a subject consuming an increased dose from the previous dose. An unsuccessful dose escalation will be defined as a subject consuming an increased dose, followed by a dose reduction. Dosing with incorrect study product will not be counted as a dose escalation nor will it be counted as an unsuccessful dose escalation. The numbers of dose escalations, unsuccessful dose escalations, dosing with incorrect study product, and dose reductions, will be listed and summarized by treatment group. In-clinic dosing, including visit, date and time, dose level, whether it was a dose reduction (and reason), and whether the dose was tolerated will be listed by subject.

To evaluate the time-course of tolerated up-dosing, the number and percent of subjects on each dose (0.5, 1, 1.5, 3, 6, 12, 20, 40, 80, 120, 160, 200, 240, or 300 mg/day) will be summarized at the End of Visit 1 and then for every 2 weeks beginning with Week 2 (Day 14), by treatment group, and presented using boxplots.

At-home dosing compliance will also be listed and summarized. Daily diary records, including date and time, whether a full or partial dose was consumed (or the dose was missed), reason for partial or missed dose will be listed. If any dose-related symptoms are present, the symptoms, onset time, and resolution time will also be listed.

The number of days of planned at-home dosing, calculated as the number of days on study minus the number of days of in-clinic dosing, will be listed by subject. For each subject, the number and percent of days for each type of dose (full dose, partial dose, and missed dose) where the percent is calculated as the number of days for that type of dose divided by the number of days of planned at-home dosing, will be listed. The number and % of days with dose-related symptoms, as recorded in the daily diary, will also be listed for each subject.

The number of days with planned at-home dosing will be summarized by treatment group and overall. The percentage of days of planned at-home dosing on which any at-home dose (i.e., full or partial) was consumed, a full dose was consumed, a partial dose was consumed, a dose was missed, or days with dosing symptoms will be summarized similarly.

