All subjects who reach and tolerate 300 mg/day for 2 weeks will undergo an exit DBPCFC. Those unable to achieve a dose of 300 mg/day of peanut protein by 34 weeks will be considered escalation failures and will not undergo an exit DBPCFC.

During the treatment period, the subjects will be monitored for tolerability as illustrated in Figure 6–1 and Figure 6–2 (see Section 6.8.4).

If a subject is removed from therapy because of failing escalation during the initial escalation period (Visit 1; Days 1 to 3), the subject will be followed for safety and asked to return to the Clinical Research Center 14 days following their last dose of study product to undergo an Early Discontinuation Visit (see Section 6.5).

If a subject's up-dosing is halted because of failing subsequent build-up (i.e., after the initial escalation period; Visit 1), the subject will continue to be dosed at the last tolerated dose level and to be followed for safety biweekly (following their established visit schedule) until Week 24, i.e., a maintenance phase (See also Section 6.8.4). Dosing will be stopped after the Week 24 Visit; and the subject will be asked to return to the Clinical Research Center 14 days following their last dose of study product to undergo an Early Discontinuation Visit (see Section 6.5).

For subjects who halt dose-escalation after Week 24, there will be no maintenance phase. Dosing in these subjects will be discontinued when dose-escalation is stopped. They will be followed for safety and asked to return to the Clinical Research Center 14 days following their last dose of study product to undergo an Early Discontinuation Visit (see Section 6.5).

For subjects who achieve the targeted dose of 300 mg/d by Week 34, the maintenance phase comprises the last two weeks of the study.

Subjects who prematurely discontinue treatment before Week 24 for any reason will be brought in for an early discontinuation visit 14 days after their last dose.

A Data Monitoring Committee (DMC) has been established and will meet every 3 months to monitor the study for safety.

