4.3.2 Follow-up of Subjects Who Discontinue Treatment Only

Subjects who prematurely discontinue treatment will be brought in for an early discontinuation visit 14 days after their last dose of study product. If possible, subjects will be monitored for safety until they come back for their Early Discontinuation Visit.

5. Study Medication

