- If not tolerated, the subject is considered an escalation failure, discontinued from treatment, and followed for safety until the Early Discontinuation Visit

Those subjects administered: 6.0 mg

- If tolerated, return home on that dose for 2 weeks until next escalation
- If not tolerated, return on Day 3 with a 1-step reduction (3.0 mg)

Day 3 Initial Escalation

Those subjects with moderate symptoms on Day 2 at the 6.0 mg dose will return on Day 3 for an observed dose. The maximum dose on Day 3 would be 3.0 mg. Those subjects administered 3.0 mg

- If tolerated, return home on that dose for 2 weeks until next escalation.
- If not tolerated, the subject is considered an escalation failure, discontinued from treatment, and followed for safety until the Early Discontinuation Visit.

5 to 10 days post-DBPCFC

• Optional post DBPCFC blood draw for exploratory analysis by ITN. The amount taken should be 5 mL/kg in children weighing ≥30 kg, with a maximum of 60 mL in total. Blood draws should be completed per NIH guidelines.

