6.8.4 Reactions During Maintenance Phase

This phase consists of the subject receiving the maximum achieved daily dose of peanut OIT.

Subjects who fail escalation during the initial escalation period (Visit 1; Days 1 to 3), i.e., subjects who do not tolerate a minimum of 3 mg of study product (CPNA or matching placebo), will stop dosing and will not enter a maintenance phase. These subjects will be followed for safety and be asked to return to the Clinical Research Center 14 days following their last dose of study product to undergo an Early Discontinuation Visit (see, **Section 6.5**).

Subjects whose up-dosing is halted because of failing subsequent build-up (i.e., after the initial escalation period; Visit 1), will continue to be dosed at the last tolerated dose level and to be followed for safety biweekly (following their established visit schedule) until Week 24. The length of time from the cessation of up-dosing to Week 24 will constitute the maintenance phase for these subjects. The maintenance phase, thus, may vary in length from subject to subject. Dosing will be stopped after the Week 24 Visit; and the subject will be asked to return to the Clinical Research Center 14 days following their last dose of study product to undergo an Early Discontinuation Visit (see, Section 6.5).

There will be no maintenance phase for subjects who halt dose-escalation after Week 24. Dosing in these subjects will be discontinued when dose-escalation is stopped. They will be followed for safety and asked to return to the Clinical Research Center 14 days following their last dose of study product to undergo an Early Discontinuation Visit (see Section 6.5).

Subjects who achieve the targeted dose of 300 mg/d by Week 34 will then enter a 2-week maintenance phase. For these subjects, the maintenance phase will be followed by a DBPCFC performed at their Exit Visit (no later than week 36; see, Section 6.5).

All subjects will continue to follow a peanut-restricted diet for the duration of the study.

For any noted symptoms during the maintenance phase, the **same** study dosing rules for the build-up phase will be followed.

Figure 6–2. Schematic for Build Up Phase Dose Escalation – Day of Symptom

6.9 Missed Peanut OIT Doses at any Phase of the Study:

Missed Peanut OIT doses at any phase of the study can pose a significant risk to the enrolled subjects. The algorithm for missed consecutive doses of study product is as follows:

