## 3.2.3 Exit Visit (Visit 03)

After approximately 24 weeks of randomized study treatment, eligible subjects who reach the targeted daily dose of 300 mg/day and maintain that dose for 2 weeks will undergo an Exit DBPCFC of up to 600 mg (1043 mg cumulative) peanut protein and placebo (see Section 6.6.2 of protocol). Subjects who have not reached 300 mg/day by Week 24 will continue to up-dose as tolerated until they are eligible for the Exit DBPCFC (after 2 weeks of at-home dosing with 300 mg/day). The Exit DBPCFC will be conducted in a manner similar to the Screening DBPCFC but with the dosing schedule as shown in Table 3.4. Note also that subjects are not scheduled for a dose of study product at home or in-clinic on the day of Visit 03.

Subjects who fail escalation, whose dose escalation is halted, and/or who prematurely discontinue treatment, will return to the site for an Early Discontinuation visit that consists of the same procedures as the Exit visit, but without a DBPCFC or associated optional blood draws. An Early Discontinuation visit is to occur 14 days from the last dose of study product.

Table 3.4. PRACTALL Exit DBPCFC

Challenge Doses					
	Peanut flour with				
Peanut Protein	50% protein content				
(mg)	(mg)				
3	6				
10	20				
30	60				
100	200				
300	600				
600	1200				

The schedule of study assessments will be as follows:

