## 8.4 Subject Disposition

Subject disposition will be recorded in the eCRF, either at the final follow-up visit or when a subject discontinues the study or is lost to follow-up. The number of subjects who enroll, complete the study, discontinue from the study, and reasons for study discontinuation will be summarized.

Number of days on study is calculated as (date of discontinuation – first dose date + 1) for subjects who discontinue the study, and (last study visit date – first dose date + 1) for subjects who complete the study. The number of days on study will be summarized for subjects who were lost to follow up.

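### SAP 10.1 counts days on study, not scheduled dosing days, as planned at-home dosing, so undosed follow-up days lower the compliance and symptom-day percentages in Table 14.1.13

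*SAP*

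**What the plan says.** SAP 10.1 sets the denominator for home compliance as days of "planned at-home dosing, calculated as the number of days on study minus the number of days of in-clinic dosing". Each subject's full-dose, partial-dose and missed-dose days, taken from the daily diary, are divided by it. Days with dosing symptoms are summarised as a percentage of the same quantity. The summary is Table 14.1.13, in the ITT population.

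Days on study is defined in SAP 8.4: "Number of days on study is calculated as (date of discontinuation" minus first dose date, plus 1, for those who discontinue the study. For completers the last study visit date takes the place of the discontinuation date. The same section says disposition is recorded "either at the final follow-up visit or when a subject discontinues the study" or is lost to follow-up.

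Dosing stops before follow-up does. SAP 3.2.3 states: "An Early Discontinuation visit is to occur 14 days from the last dose of study product". Protocol 4.3.2 says that, if possible, "subjects will be monitored for safety until they come back for their Early Discontinuation Visit". Protocol 6.4.1 has subjects who fail at Visit 01 "discontinued from treatment, and followed for safety until the Early Discontinuation Visit", and Protocol 6.8.4 says such subjects "will stop dosing and will not enter a maintenance phase". After a later build-up failure before Week 24, "the subject will continue to be dosed at the last tolerated dose level" until Week 24 (Protocol 3.2), and the 14-day visit follows. For completers, SAP 3.2.3 notes that no dose is scheduled, at home or in clinic, on the day of Visit 03.

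**The concern.** The formula does not measure what it is named for. Days on study can extend past the last day on which a home dose was due, and nothing in SAP 10.1 removes the excess. For a subject who stops early, the reported percentage then mixes non-adherence with days when nothing was scheduled. The full, partial and missed shares no longer sum to 100%, because follow-up days have no diary entry.

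The SAP does not define the date of discontinuation. SAP 12 lists last dose, last study visit and discontinuation/termination as separate dates, while Table 7.1 has a category for subjects discontinued during initial escalation. The programmer would have to choose.

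Two further cases have no rule. Visit 01 failures have taken study product, so they are in ITT, but no home dosing was ever scheduled for them. Addendum 2.3 removes product taken after the exit challenge from the compliance summaries, while noting that those subjects stayed enrolled in ARC001; it does not say that the matching days leave the denominator. Addendum 2.4 only sets the value of a partial dose.

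At stake is the reading of the planned summary of home compliance and symptom-day percentages. The distortion is largest for those who stop earliest.

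**Working it through.** The plan gives no figure to reproduce, so this applies its definitions to example subjects.

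**Inputs**
- Denominator: SAP 10.1 and 8.4.
- Interval from last dose to the Early Discontinuation visit: 14 days (SAP 3.2.3; Protocol 3.2, 4.3.2).
- Clinic dosing: every 2 weeks (SAP 3.2.2).
- Assumed: first dose on day 1, two-day Visit 01, next clinic doses on days 15, 29 and so on, and full adherence unless stated.

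**Formulas**, with L = study day of last dose and G = days from last dose to the date used
- In-clinic days C = 2 + floor((L − 1)/14)
- Home days actually scheduled H = L − C
- SAP denominator = (L + G) − C = H + G
- Reported share for a fully adherent subject = H/(H + G)

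| Last dose day | C | H | G = 14 | G = 7 (assumed) | G = 0 |
|---|---|---|---|---|---|
| 28 | 3 | 25 | 25/39 = 64.1% | 25/32 = 78.1% | 100% |
| 84 | 7 | 77 | 77/91 = 84.6% | 77/84 = 91.7% | 100% |
| 168 (dosed to Week 24) | 13 | 155 | 155/169 = 91.7% | 155/162 = 95.7% | 100% |

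Counting one more clinic day in each row gives, for G = 14, 24/38 = 63.2%, 76/90 = 84.4% and 154/168 = 91.7%. Symptom-day percentages shrink by the same factors.

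**Visit 01 failure on Day d (1, 2 or 3).** Dated at the 14-day visit: (d + 14) − d = 14 planned days, so 0/14 = 0%. Dated at Visit 01: d − d = 0, so the share is undefined.

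**Completer, last dose day 154.** C = 12, H = 142.
- One-day challenge: 142/143 = 99.3%.
- Two-day challenge: 142/144 = 98.6%.
- Two-day challenge plus 7 assumed on-study days afterwards: 142/(142 + 2 + 7) = 142/151 = 94.0%.

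**Subject stopped for missing more than 7 consecutive days (Protocol 6.9).** Last dose day 20; clinic days 1, 2 and 15; home doses 17; days 21–28 missed (8 days); next clinic day would be 29.
- Scheduled home days = 17 + 8 = 25. Full 17/25 = 68.0%, missed 8/25 = 32.0%.
- SAP rule dated at day 34: denominator 34 − 3 = 31. Full 17/31 = 54.8%, missed 8/31 = 25.8%, total 80.6%. Six unscheduled days (29–34) were added.
- Dated at last dose: denominator 20 − 3 = 17. Full 17/17 = 100%, which hides the missed days.

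**Arm mean (illustrative).** 25 per arm, everyone else at 100%, and 3 or 5 subjects without an exit challenge (the planning numbers in SAP 4), each with G = 14:
- All last dosed day 168: (22 × 100 + 3 × 91.7)/25 = 99.0%; (20 × 100 + 5 × 91.7)/25 = 98.3%.
- All last dosed day 28: (2200 + 3 × 64.1)/25 = 95.7%; (2000 + 5 × 64.1)/25 = 92.8%.
- All Visit 01 failures entered as 0%: 2200/25 = 88%; 2000/25 = 80%.

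**The case against.** **The early-stopper effect depends on an eCRF date that the documents do not define.** This stands. The discontinuation categories in SAP Tables 7.1 and 7.2 could be read as dating discontinuation when treatment stops, and then the 14-day tail vanishes. But SAP 8.4 speaks of discontinuing the study, and Protocol 6.4.1 separates stopping treatment from the end of follow-up. The completer's challenge day does not depend on this date at all.

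**The direction could differ.** If blank follow-up days were programmed as missed, the missed share would be too high. SAP 10.1, however, treats missed as something recorded in the diary, so on its natural reading blank days enter the denominator only. A last-dose date can make the full-dose share too high, as the 100% against 68.0% example shows. That is a reason not to cut at the last dose.

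**The arm-level effect is usually small.** This is fair. Build-up failures halted before Week 24 stay on dose until then, which gives an arm mean of 98.3% to 99.0% in the illustration. Larger shifts need most stoppers to leave very early, and the median, also reported, would move little.

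**The listings let a reader correct it.** Planned days, dose counts and treatment duration are listed by subject, so the error can be traced. The summary table is still wrong as specified.

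**Addendum 2.3 naturally implies dropping the matching days.** That is a sensible implementation, but it is not written.

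**Conclusion.** The concern holds, as a minor point. As written, the SAP counts undosed days as planned home dosing. The effect for completers is small: 0.7 to 1.4 percentage points in the day-154 example. It relies on the SAP 3.2.3 statement that no dose is scheduled on the Visit 03 day. For early stoppers the loss ranges from none to 35.9 points (100 − 64.1) in the examples, depending on which date is used and when dosing stopped. Visit 01 failures get 0% or an undefined value.

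Confidence is moderate, because the eCRF date definition and the distribution of stopping times are not in the documents. The table is descriptive: efficacy analyses, responder status and the symptom-day counts in SAP 10.7 are unaffected. No difference between arms follows unless early stopping is unequal, and the documents do not show that.

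**What to change.** In SAP 10.1:
- End planned at-home days at the last date on which a dose was scheduled before the exit challenge or before treatment was stopped, derived from the diary and dispensing records. Subtract the in-clinic dosing days within that span.
- Keep trailing days that were scheduled but missed. Do not simply substitute the last-dose date or the treatment duration.
- Remove days after the exit challenge from the denominator as well as the numerator.
- Show percentages as not applicable when planned home days are zero.
- State a convention for diaries that simply stop, for example on loss to follow-up.

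SAP 10.7 needs no change. The cost is about one SAP sentence, a footnote to Table 14.1.13 and a small amount of programming. The real work is the derived end date, since the documents name no field for the last scheduled dose.
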